### ***Inclusion Criteria***

- Ages 18-65 years
- English speaking

- Healthy, Non-treatment-seeking community members who do not have a mental health diagnosis and individuals seeking treatment for an anxiety, mood, trauma-related, or obsessive-compulsive disorder.
- Treatment and non-treatment-seeking community members with anxiety, mood, trauma-related, or obsessive-compulsive disorder or symptoms.
- Patients at MUSC who have received implanted VNS for depression or stroke recovery.

#### ***Exclusion Criteria***

- Diagnosis of COVID-19 in the past 14 days
- Facial or ear pain or recent ear trauma for the taVNS group only.
- Metal implant devices in the head, heart or neck for the taVNS group only.
- History of brain stimulation or other brain surgery for the taVNS group only.
- History of myocardial infarction or arrhythmia, bradycardia for the taVNS group only.
- Use of B-blockers, antiarrhythmic medication (sodium/potassium/calcium-channel blockers), or blood pressure medications for the taVNS group only.
- Active respiratory disorder for the taVNS group only.
- Personal or family history of seizure or epilepsy or personal use of medications that substantially reduce seizure threshold (e.g., olanzapine, chlorpromazine, lithium).
- Personal history of head injury, concussion, or self-report of moderate to severe traumatic brain injury for the taVNS group only.
- Individuals suffering from frequent/severe headaches for the taVNS group only.
- Individuals with lifetime evidence of severe psychiatric disorder (e.g., schizophrenia) or neurological disorder for the taVNS group only.
- Moderate to severe alcohol or substance use disorder.
- Pregnancy

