Participants will be randomized to one of 9 dose durations with 5 participants per dose, increasing in 10 minute increments of active stimulation, ranging between 10 and 90 minutes of stimulation. All active sessions per dose will be delivered contiguously and at the end of the stimulation period, and sham stimulation at the beginning. This is to ensure that all participants have the same lapse of time between pre- and post-stimulation recording. That is, if a participant is randomized to 60 minutes of active stimulation, the first 30 minutes would be sham stimulation. After establishing the optimal dose-duration a sample of treatment seeking individuals will be recruited. This dose will be administered to individuals with anxiety and trauma symptoms to ensure that effects are sustained and to determine feasibility and tolerability.

An additional group of individuals with implanted VNS also will be evaluated after 30 minutes of stimulation. Patients at MUSC who participated in the Microtransponder Vivistim trial or other research/treatments involving VNS will be recruited to complete similar cognitive and affective tasks while psychophysiological responses are measured across 3 sessions: control (no stimulation), implanted VNS, and noninvasive taVNS. This will serve as a comparator for whether taVNS is activating similar brain and physiological regions as invasive forms of vagus nerve stimulation. This will also indicate whether mechanisms of taVNS and VNS are comparable. In order to truly determine comparability of these two forms of VNS, it is imperative to assess within subject brain, body, cognitive, and emotional responding across both implanted and non-invasive VNS.

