After all electrodes are attached, a 1) baseline (5-10 min) physiology measurement will be taken. Then stimulation will begin. See additional information in Section 3.0 (Intervention to be Studied). Participants in the taVNS group (not having implanted VNS) will be randomized to one of 9 doses with 5 participants per dose, increasing in 10 minute increments of active stimulation. All active sessions per dose will be delivered contiguously and at the end of the stimulation period, and sham stimulation at the beginning. This is to ensure that all participants have the same lapse of time between pre- and post-stimulation recording. That is, if a participant is randomized to 60 minutes of active stimulation, the first 30 minutes would be sham stimulation.

For participants with previously implanted vagus nerve stimulation devices, stimulation will be delivered for 30 minutes. They will subsequently be invited to revisit the lab to receive non-invasive taVNS delivered in a comparable manner to the healthy subjects for 30 minutes.

Additional physiology measurements will be taken 2) concurrent with stimulation and during a final recovery measurement (5-10 mins) after stimulation has concluded.

During the base, recovery, and during 3 time points during the 90-minute stimulation period (i.e., 30 minutes, 60 minutes, and 90 minutes), a Passive Auditory Oddball Task will be administered. During this task a relaxing movie (i.e., silent sand art film) is presented concurrent with standard and deviant tones; MMN task from the ERP Compendium of Open Resources and Experiments - ERP CORE; Kappenman et al., 2020; Eriksen & Eriksen 1974).

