For participants with previously implanted VNS devices, the same Passive Auditory Oddball task will be administered. Additional tasks will be administered, including a visual search task, during which an array of shapes are presented on a computer screen. Participants must identify and click on a target shape (N2pc task from the ERP Compendium of Open Resources and Experiments - ERP CORE; Kappenman et al., 2020). A cued picture viewing task will be administered consistent with other research at MUSC department of psychiatry studies. Cues (shapes) are presented followed by either an unpleasant, pleasant, or neutral picture. Pictures are from the International Affective Picture System (Lang et al., 2005). Similar research is being conducted at MUSC by co-investigator [name] using these pictures and task design. Finally, a fear learning and extinction task will be administered. Participants will see different shapes/colors appear on the computer screen. Some of the shapes/colors will be paired with the sound of a person screaming (Glen et al., 2012). White noise bursts will be played during these tasks at random times.

During the physiology/task assessment participants will be provided with a brief break from computer tasks. During this time, the Montreal Cognitive Assessment (MOCA; Nasreddine, 2004) will be administered to ensure there is no major cognitive decline.

Then a 3) finally during a recovery period (5-10 min) resting physiology measurement will be taken. After all the tasks are completed, participants will be debriefed about the purpose of the study, compensated for their time, and released. Participants will be reimbursed using a ClinCard with the amount of \$100. They will be provided with the ClinCard along with relevant information (e.g., ATM withdrawal fees, how to use) prior to leaving the in-lab procedures.

Participants with implanted VNS will be asked to return for a second visit, during which they will receive no stimulation, but will be asked to complete the same tasks. The order of stimulation versus no

stimulation lab visits will be randomized. They will be reimbursed using a ClinCard with the amount of \$180 for the first 2 lab visits and surveys. Should participants with implanted devices agree to a third in-lab visit for 2.5 hours, they will be reimbursed with an additional \$80.00 to their ClinCard.

Several procedures will be taken to minimize risks over the course of the study:

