**VNS:** Participants being recruited to complete this study with VNS, will include subjects with previously implanted devices and who have been given permission by their physician to activate their own stimulator without health risks. These participants who may administer their own stimulation have been given a “magnetic wand” or button to activate their stimulator in order to encourage post-stroke motor function. No severe adverse effects have been reported with implanted devices after implantation. However, mild discomforts/risks have been reported including nausea and dysphagia (swallowing difficulties) which resolve by the end of the day after stimulation. Participants will be encouraged to report discomfort and will be assessed periodically for these discomforts. To ensure that ongoing VNS treatment is not affected, only those who have completed VNS treatment/research or whose VNS treatment/research will not be affected by 30 minutes of stimulation will be recruited for the study.

**Surveys:** Some report mild discomfort when reporting on these topics, so study staff, including the PI and Co-I, will be available to debrief participants in distress, if needed. The PI will be available to provide counseling resources if participants are interested, and in the case of suicidal ideation and intent (see Section 13.0) immediate and appropriate response will be provided, including encouraging the participant to remain with experimenters (even if study is terminated) to ensure the participant is in a safe location. The study personnel are clinically trained to identify participants in distress. However, these surveys involve minimal and low-base rate for risk.

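### Implanted-VNS patients may receive 30 minutes of taVNS, but the cardiac, drug and ear exclusions do not apply to them and their physician clearance does not extend to taVNS

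*Combined protocol and SAP*

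**What the plan says.** **Eligibility.** The exclusion list in Section 5.0 includes "History of myocardial infarction or arrhythmia, bradycardia for the taVNS group only". The next item covers beta-blockers and antiarrhythmics and ends "or blood pressure medications for the taVNS group only". Facial or ear pain and recent ear trauma carry the same limit.

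**Who the taVNS group is.** Section 10.0 states it in a parenthesis: "Participants in the taVNS group (not having implanted VNS) will be randomized to one of 9 doses".

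**What implanted patients receive.** Section 3.0 plans that their "psychophysiological responses are measured across 3 sessions: control (no stimulation), implanted VNS, and noninvasive taVNS". Section 10.0 says that after the session with their own device they will be "invited to revisit the lab to receive non-invasive taVNS delivered in a comparable manner to the healthy subjects for 30 minutes". The first two visits are the stimulation and no-stimulation visits, in random order. The remaining one depends on consent: "Should participants with implanted devices agree to a third in-lab visit for 2.5 hours".

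**Clearance.** Under the VNS risk text of Section 10.0, the implanted patients recruited are those "who have been given permission by their physician to activate their own stimulator without health risks". Section 13.0 adds that their doctors must have cleared them for 30 minutes of unmonitored stimulation at home, at the settings they already use there.

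**Other safeguards.** At set-up, Section 10.0 asks participants what medication they take and when they last took it, attaches ECG, and records a physiological baseline of 5 to 10 minutes before stimulation. Section 13.0 provides for safety monitoring of the physiological data and for physicians to be available if an adverse event occurs.

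**The concern.** A healthy volunteer with a history of arrhythmia, or one taking a beta-blocker, cannot receive taVNS in this study. A patient with an implant and the same history or drug can, because the wording that lets implanted patients into the study also lifts these exclusions for them. The protocol gives no reason for treating the two differently when the stimulation is the same.

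Section 5.0 justifies its exclusions on grounds of participant safety, and Section 4.0 notes that taVNS has slowed heart rate under some parameters. The ear criterion matters for a simpler reason: the tragus is the stimulation site, and ear trauma or pain is one of the examples Sections 10.0 and 15.0 give when they mention contraindications to taVNS.

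At stake is whether someone decides, before the taVNS visit, that taVNS is suitable for that patient. The dose-response analysis is not affected.

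**Working it through.** The point is textual. The only arithmetic is a count and a proportion.

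1. **Count the limited exclusions.** Section 5.0 lists 13 exclusions. Nine are limited to the taVNS group: ear or facial pain or trauma; metal implants; prior brain stimulation or brain surgery; myocardial infarction, arrhythmia or bradycardia; rate and blood-pressure drugs; respiratory disorder; head injury; headaches; and severe psychiatric or neurological disorder. The other 13 − 9 = 4 apply to everyone: recent COVID-19, seizure history or threshold-lowering drugs, alcohol or substance use disorder, and pregnancy.

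2. **Apply the definition.** Section 10.0 equates the taVNS group with not having an implant. All nine limited exclusions therefore fall away for implanted patients, including at the visit where they receive taVNS.

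3. **Test the other reading.** Suppose *taVNS group* meant anyone given taVNS. The criterion "History of brain stimulation or other brain surgery for the taVNS group only" would then bar every implanted patient, because Section 1.0 treats VNS as a form of brain stimulation. The metal-implant criterion would probably do the same, though the documents do not describe where the device sits. The neurological-disorder criterion could bar the stroke-recovery patients whom Section 5.0 invites. The taVNS session in Section 3.0 could not take place, so this reading does not fit the plan.

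4. **Sort the nine waivers.** Prior brain stimulation must be waived for the cohort to exist, and metal implants and neurological disorder very plausibly must be too. No such need applies to cardiac history, cardiac and blood-pressure drugs, or ear and facial pain or trauma.

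5. **Look for a substitute check.**
   - Sections 10.0 and 13.0: the clearance is for the patient's own stimulator.
   - Section 8.0: clinicians are asked to invite patients whose VNS treatment or research is finished or would not be disturbed. That protects the VNS protocol and does not assess fitness for taVNS.
   - Sections 10.0 and 15.0: both promise screening for taVNS contraindications, but refer to Section 5.0 for the criteria.
   - Section 10.0, set-up: medication is recorded. No cardiac-history question is named, and no answer is tied to proceeding or seeking clearance.
   - Section 13.0: physicians respond to events, which is not a screen beforehand.

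6. **Size.** Section 6.0 plans 45 healthy, 40 symptomatic and 5 implanted participants, 90 in all. Affected: at most 5/90 = 5.6%. Section 1.0 expects fewer than 5, which gives at most 4/90 = 4.4%. Patients who decline the third visit reduce this further. The remaining 45 + 40 = 85 are covered by the exclusions as written.

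**The case against.** The strongest reply is that these patients are far from unobserved. Their drugs are asked about before stimulation, ECG is attached and a baseline is taken, heart rate is measured continuously (Section 4.0), discomfort and adverse events are assessed during stimulation, and physicians are available. Section 13.0 cites earlier work at the same parameters that reported no adverse events, with heart rate among the things assessed. The visit is optional, serves an exploratory aim, and involves very few people.

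Most of this stands. A reader might infer that a patient with an excluded condition or drug could receive taVNS with nobody recording it. The documents do not support that: the medication question already captures the drug criterion, and the ECG would be running. A reader might also infer that harm is likely. The documents do not support that either. They give no rate of these conditions among implanted patients, so any probability of exposure would rest on an assumed prevalence and would be no evidence of size.

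Two things survive. Recording a drug is not the same as acting on it, and no rule says what follows from the answer. The earlier work is reassuring, but the documents do not say that it included people with these cardiac conditions or with implants.

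A further reply is that the phone screener may put every Section 5.0 question to every caller. The documents do not show its items. Even if it does, an implanted patient who answered yes would still be eligible, because the criteria are not theirs.

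**Conclusion.** The gap holds as a point of eligibility and safety wording, of minor severity. Implanted patients may receive taVNS without the cardiac-history, drug and ear criteria applying to them, and without clearance that extends to taVNS. The deficiency is the absence of a named cardiac-history question and of any rule linking the available information to a decision about taVNS. The drug and ECG data themselves are collected.

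It affects at most 5 of 90 participants, and only those who accept the third visit. The share who would meet a criterion is unknown. The conclusion rests on taking the parenthesis in Section 10.0 as the meaning of the taVNS group in Section 5.0, which is the only reading found under which the planned taVNS session can occur. It does not bear on the sample size, the MCP-Mod analysis or any estimate for Aims 1 to 3.

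**What to change.** Add to Section 5.0:

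> Before the taVNS visit of a participant with implanted VNS, staff will record any past myocardial infarction, arrhythmia or bradycardia; any current beta-blocker, antiarrhythmic or blood-pressure drug; and any pain in the face or ear or recent injury to the ear. A participant with such pain or injury will not receive taVNS. A participant who meets a cardiac or drug criterion will receive taVNS only with documented clearance for taVNS itself from the treating physician or a Brain Stimulation Lab physician. All other exclusions limited to the taVNS group, including those for metal implants, prior brain stimulation and neurological disorder, remain waived for these participants.

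The last sentence should name the retained waivers. Listing only some of them could cast doubt on the rest and put the stroke-recovery patients' third visit in question.

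Nothing needs to be added to Section 13.0, since heart rate is already recorded and physiological data are already monitored for safety.

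**Cost.** A short record for each of at most 5 people, part of which the set-up medication question already supplies; a clearance note for those who meet a cardiac or drug criterion; and possibly the loss of some optional third visits. Each lost visit removes one within-patient comparison of taVNS with implanted VNS from Exploratory Aim 3, which is a real loss in so small a group. The comparison stays possible for everyone else.

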## **6.0 Number of Subjects**

This study will recruit 90 community individuals who meet the above inclusion and exclusion criteria, 50% of which will be female. Participants ( $n = 45$ ) who are healthy controls will be recruited to establish the dose response curve. Then this dose will be administered to 40 individuals with anxiety and trauma related symptoms. Participants with implanted VNS ( $n = 5$ ) will be recruited for similar procedures.

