In order to develop therapeutic taVNS for psychiatric problems, a necessary first step is to establish the appropriate parameters that will modulate cognitive and affective responses among healthy participants. We will first recruit 45 healthy participants (randomized to 9 different dose durations) to determine the dose-response curve for taVNS on a range of vagally-mediated physiological measures and subjective mood. At a single session, heart rate variability (HRV), skin conductance (SC), and electroencephalography (EEG) will be measured at baseline, concurrently with stimulation, during learning and cognitive tasks and finally during a recovery period. Utilizing rest, learning and recovery conditions concurrent with multiple physiological measures we will demonstrate whether there is process- or physiological modality-specific modulation or co-activation across domains and measures. Our team of experts in brain stimulation, neuroscience, and psychophysiology are uniquely suited to accomplish these tasks. After establishing the dose-response curve, the findings of our dosing may be evaluated an additional sample of 45 participants seeking treatment for anxiety or trauma related disorder.

An additional goal of this study is to evaluate invasive vagus nerve stimulation (VNS) to determine how taVNS relates to other established forms of brain stimulation via the vagus nerve. VNS is currently FDA approved for depression and epilepsy, and research has indicated that patients also report decreased anxiety symptoms. Therefore, patients with previously implanted VNS, will be invited to complete this study. They will be administered similar tasks as participants who receive taVNS, and a full psychophysiological profile will be assessed. This study will only recruit individuals who currently have implanted VNS, given the invasive procedure. Although VNS is FDA approved, nearly 150,000 patients have received VNS worldwide over the past 25 years. Therefore, limited patients in the study area have received VNS, so this study expects to recruit <5 patients for this study goal.

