## 12.0 Data Management

Power: Dose-response studies are not powered in the traditional manner. To resolve the shape of the continuous dose response function, it is statistically more efficient to select more doses as opposed to more participants (O’Quigley & Conaway, 2010; Kuljus et al., 2006). The number of observations within each dose primarily accounts for sampling variability, which could be achieved with 2-3 observations. Capturing variability is essential to the planned analyses, which underweight the points of greatest variability in estimating the response curve. Thus, the sample size of  $N = 45$  was determined sufficient to accomplish Aim 1 to establish a dose-response curve. Of note, [name] is running three funded projects with these dose-response techniques in optimizing repetitive transcranial magnetic stimulation (rTMS). An additional, sample of 45 participants are included in the case of data loss and to replicate dose-response findings/assess feasibility/tolerability on participants with anxiety or trauma related disorder or symptoms.

Analyses: The psychophysiological data will be processed using standard protocols which have previously been used in this lab and in various other studies (Sege et al., 2017, 2018, Taylor et al., 2020; Grant et al., 2015), and according to published guidelines (Blumenthal et al., 2005; Boucsein et al., 2012; Gatchel et al., 1973; Keil et al., 2014).

Dose-response relationships will be assessed using the multiple comparisons procedure with modeling (MCP-Mod) approach pre- to post-stimulation changes in physiology and behavior. To determine the reliability of a dose response, MCP-Mod fits a set of pre-specified candidate dose-response curves to the data using a multiple-comparisons technique. The pre-specified dose-response curves to be tested would be Emax, logistic, and linear. Significant curves would then be used to develop inferences on optimal doses for a follow-up adaptive-dosing design, with doses more finely resolved around the probable point of maximal efficacy as determined in this project.

**Confidentiality and Quality Control:** All study personnel will complete Social-Behavioral-Educational research CITI training, and also complete in-lab training regarding data security practices. Study personnel will be trained in the IRB protocol. The investigator, and co-investigators will be available to monitor data collection to ensure quality, confidentiality, and adherence to the IRB protocol.

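### The anxiety/trauma cohort is planned as 45 in Sections 1.0 and 12.0 but 40 in Section 6.0, and the implanted-VNS group is fewer than 5 in one place and 5 in another

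*Combined protocol and SAP*

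**What the plan says.** Three sections of the combined protocol and SAP give planned numbers.

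- **Section 1.0 (Objectives / Specific Aims)** starts with the dose-finding cohort: "We will first recruit 45 healthy participants (randomized to 9 different dose durations". It then says that "the findings of our dosing may be evaluated an additional sample of 45 participants seeking treatment for anxiety or trauma related disorder". A separate paragraph introduces patients who already have an implanted stimulator as a further goal, notes that few live in the study area, and concludes: "so this study expects to recruit <5 patients for this study goal".
- **Section 6.0 (Number of Subjects)** is the only place that states a total: "This study will recruit 90 community individuals who meet the above inclusion and exclusion criteria". It divides this into 45 healthy controls, the anxiety/trauma cohort ("Then this dose will be administered to 40 individuals with anxiety and trauma related symptoms") and n = 5 with implanted VNS.
- **Section 12.0 (Data Management)**, under Power, takes N = 45 as sufficient for Aim 1 and adds: "An additional, sample of 45 participants are included". It gives this second 45 two purposes: cover for data loss, and replication with assessment of feasibility and tolerability in people with anxiety or trauma disorders or symptoms. It does not mention implanted patients.

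Section 3.0 confirms the structure of the first cohort: "Participants will be randomized to one of 9 dose durations with 5 participants per dose".

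**The concern.** The planned size of the cohort that serves Aim 3 (tolerability and feasibility in anxiety and trauma) differs by 5 between sections, and the implanted group differs by at least 1. Nothing in the document reconciles the figures.

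This matters more than a slip in wording usually would, because Section 12.0 gives no alpha, power, effect size, standard deviation or precision target for any cohort. The planned count is therefore the only quantitative commitment the plan makes for Aim 3. If it is left open, recruitment could close at 40 or at 45 and either would agree with some part of the plan. A number fixed beforehand removes that choice. The data-loss role in Section 12.0 adds to the uncertainty, since the plan does not say how many of the second 45 are replacements and how many are the Aim 3 cohort proper.

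**Working it through.** **Inputs**

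| Cohort | Section 1.0 | Section 6.0 | Section 12.0 |
|---|---|---|---|
| Healthy, dose-finding | 45 | 45 | 45 |
| Anxiety/trauma | 45 | 40 | 45 (also cover for data loss) |
| Implanted VNS | fewer than 5 | 5 | not mentioned |
| Stated total | none | 90 | none |

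**Step 1. Reproduce the plan's own figures.** The dose-finding cohort is 9 doses × 5 per dose = 45, which agrees in every section. The Section 6.0 total is 45 + 40 + 5 = 90, as stated.

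**Step 2. Compare across sections.** Anxiety/trauma: 45 − 40 = 5, and 5/45 = 11%. Implanted: at most 4 against 5, a gap of at least 1.

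**Step 3. Add up the alternatives.** Here fewer than 5 is taken as 1 to 4.

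- Section 1.0 components, implanted patients additional: 45 + 45 + (1 to 4) = 91 to 94.
- Anxiety/trauma 45 with the 5 implanted of Section 6.0: 45 + 45 + 5 = 95.
- Anxiety/trauma 40 with the implanted expectation of Section 1.0: 45 + 40 + (1 to 4) = 86 to 89.
- Second 45 taken as already containing the implanted patients, or implanted patients not counted in the total: 45 + 45 = 90.

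The two blocks of 45 in Section 12.0 therefore match the 90 of Section 6.0 only if implanted patients sit inside the second block or outside the total. The document states neither.

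**Step 4. What the gap of 5 means for Aim 3.** The plan sets no tolerability rate or precision, so both scenarios below are assumptions chosen to show scale.

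- No events observed, one-sided 95% upper bound, 1 − 0.05^(1/n): at n = 40, 1 − 0.05^(1/40) = 7.2%; at n = 45, 1 − 0.05^(1/45) = 6.4%. Difference: 0.8 percentage points.
- Observed proportion of 0.5, 95% half-width, 1.96 × √(0.25/n): at n = 40, 15.5 points; at n = 45, 14.6 points. The ratio of standard errors is √(45/40) = 1.06.

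**The case against.** The best defence is that the second 45 is simply 40 + 5. Section 12.0 has two blocks of 45, which make the 90 of Section 6.0, and the second block in Section 6.0 is 40 + 5. An implanted group added later, with Sections 1.0 and 12.0 left as they were, would produce exactly this pattern. That is the likely history, and the text does not rule it out. It is still an inference. Section 1.0 describes its 45 as people seeking treatment for anxiety or trauma, then gives the implanted patients a separate goal and a separate number. Section 5.0 admits them on a separate criterion, an implant for depression or stroke recovery. Nor does the 40 + 5 reading settle fewer than 5 against 5.

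It is also fair to say that the implanted figure in Section 1.0 is an expectation, that its gap could be a single patient in an exploratory comparison, and that Section 1.0 says only that the findings may be evaluated in the second sample. These points reduce the weight of the discrepancy but do not reconcile the numbers.

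A reader might infer four stronger things, none of which the document supports:

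- *That the total of 90 is an arithmetic error.* It is not; it equals the sum of the components in Section 6.0.
- *That the approved total is either 90 or 94.* No section states any total but 90. The 94 is only the upper end of a sum of Section 1.0 components, and nothing says what total was approved.
- *That Aim 3 rates would lack a denominator, or that a stated precision would worsen.* Observed rates would be divided by the number actually treated, and no Aim 3 precision is stated.
- *That calling all 90 community individuals excludes the implanted patients.* The same sentence refers to the eligibility criteria, which list them, so this is loose wording.

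**Conclusion.** The inconsistency stands. The anxiety/trauma cohort is 45 in two sections and 40 in a third, a gap of 5 or 11%; the implanted group is fewer than 5 in one section and 5 in another. Section 6.0 is correct within itself, so the disagreement lies between sections. The excess over 90 in Section 1.0 (up to 94) depends on counting implanted patients in addition to the second 45, which is the natural reading of that section but is not stated.

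The practical size is modest: 0.8 percentage points on a zero-event upper bound, under a scenario that the plan does not itself set. Aim 1 and its 9 × 5 allocation are untouched. It should still be corrected, because a planned sample size is a figure that the trial relies on and here it has two values.

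**What to change.** State one planned number for each cohort (healthy, anxiety/trauma, implanted VNS) and one total, in identical terms in Sections 1.0, 6.0 and 12.0. Say explicitly whether implanted patients count within the 90 and whether participants recruited to replace lost data do.

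- If Section 6.0 governs, change the anxiety/trauma figure from 45 to 40 in Sections 1.0 and 12.0, and align the two implanted figures, for example as up to 5.
- If 45 governs, change the 40 in Section 6.0 and restate the total to match: 45 + 45 = 90 before any implanted patients are added.

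In either case, Section 12.0 should separate the Aim 3 cohort from the allowance for data loss. The cost is wording only; no design feature or analysis changes. If the sponsor keeps 40, the zero-event bound is 7.2% where 45 would give 6.4%.
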